6.12. Safety Analyses.....	11
6.12.1. Extent of Exposure.....	11
6.12.2. Adverse Events	11
6.12.3. Deaths, Other Serious Adverse Events, and Other Notable Adverse Events	12
6.12.4. Clinical Laboratory Evaluation.....	12
6.12.5. Immunogenicity	13
6.12.6. Vital Signs and Other Physical Findings.....	14

6.12.7. Electrocardiograms	14
6.13. Subgroup Analyses.....	14
6.14. Protocol Deviations	14
6.15. Interim Analyses and Data Monitoring	14
6.16. Planned Exploratory Analyses.....	15
6.17. Totality of Evidence for Safety.....	15
6.18. Annual Report Analyses.....	16
6.19. Clinical Trial Registry Analyses	16
7. Unblinding Plan	18
8. Reports to be Generated at Final Database Lock.....	19
9. References	21
10. Appendices	22

Table of Contents

Appendix		Page
Appendix 1.	Planned Laboratory Analytes and Direction of Interest	23

3. Revision History

SAP Version 1 was approved prior to unblinding data for H0P-MC-BP01.

SAP Version 2 was approved prior to unblinding H0P-MC-BP01 data for PoC lock. The following updates were made.

- Section 6.1, the estimand for this ISA was described.
- Section 6.10.3, the details for the constrained model for the key secondary endpoint were added.
- Section 6.17, section added to describe the safety totality of evidence analysis.

SAP Version 3 was approved prior to the final lock. The following updates were made.

- Section 6.11, bioanalytical and pharmacokinetic/pharmacodynamic analysis was updated.
- Section 6.12.2, definition for post-treatment-emergent adverse events was updated.
- Section 6.12.4, the analysis for renal function assessment was updated.
- Section 6.12.5, immunogenicity analysis was added.
- Section 6.14, ‘violations’ is replaced with ‘deviations’ for consistency across CPMP documents, and the list of IPDs is referenced in the trial issue management plan. The prohibited medications and drugs of abuse list was moved to the CPMP SAP because it applies across all ISAs, and acetylsalicylic acid was added to the list of prohibited medications.
- Section 7, text on maintaining the blind for assessment committee review was deleted from BP01 SAP V3 since it is covered in H0P-MC-CPMP SAP Version 5.
- Section 8, additional analyses for the double-blinded treatment and safety follow-up period combined was added for the final lock.

4. Study Objectives

4.1. Primary Objective

The primary objective of this ISA is stated in the H0P-MC-CPMP (a) protocol. For H0P-MC-BP01, endpoint is defined as 8 weeks post initial treatment administration.

4.2. Secondary Objectives

Secondary objectives applicable to all ISAs are listed in the H0P-MC-CPMP SAP Version 5.

Additional secondary endpoints specific to H0P-MC-BP01 are listed below.

Objective	Endpoint Measure
Other Secondary	
Physical Functioning Efficacy of LY3016859 versus placebo	
 Mean change from baseline to endpoint for the Roland-Morris Disability Questionnaire (RMDQ) total score Proportion of participants with reduction from baseline of at least 3.5 points on RMDQ total score across all time points Proportion of participants with reduction from baseline greater than or equal to 30%, 50%, and 70% on the RMDQ total score across all time points Time to first treatment response with at least 30%, 50%, and 70% reduction from baseline in RMDQ total score

4.3. Exploratory Objectives

The following exploratory objectives and endpoints are specific to H0P-MC-BP01.

Objectives	Endpoints
Tertiary/Exploratory	
Characterize the pharmacokinetics and pharmacodynamics of LY3016859 after multiple intravenous infusions in participants with CLBP	Assessment of serum concentrations of LY3016859 and epiregulin to enable pharmacokinetic and pharmacodynamic evaluations
Characterize immunogenicity of LY3016859	Appearance of treatment emergent anti-drug antibodies and neutralizing antibodies to LY3016859
Explore the effect of LY3016859 on the kidney	
Assessment of
 
 urine albumin/creatinine ratio urine protein/creatinine ratio eGFR

Abbreviations: eGFR = estimated glomerular filtration rate.

5. Study Design

5.1. Summary of Study Design

The H0P-MC-CPMP SAP Version 5 provides a summary of the overall study design for the chronic pain master protocol. This section describes ISA-specific study design components.

Post-treatment Follow-up Period (Visits 801-803)

Participants must complete 3 post-treatment follow-up visits for safety, PK and immunogenicity assessment at Visits 801-803, according to the Schedule of Activities (SoA).

The site schedules Visit 801 approximately 4 weeks after Visit 7, Visit 802 approximately 8 weeks after Visit 7, and Visit 803 approximately 18 weeks after Visit 7.

If the participant receives at least one dose of intervention and discontinues during the double-blind treatment period, they should complete early discontinuation procedures per the CPMP Protocol SoA, and Visit 801 should be scheduled approximately 30 days after the last dose of study intervention

5.2. Determination of Sample Size

Approximately 150 participants will be randomized in a 2:1 ratio to LY3016859 and placebo, respectively. It is expected that approximately 128 participants will complete the double-blind treatment period of the study. **CCI**

CCI

[REDACTED]. If there is no treatment difference between placebo and LY3016859, the probability of passing the efficacy criterion specified above (i.e., false positive) is less than 0.05. The simulation for the power calculation and sample size determination was carried out in FACTS Version 6.0.

5.3. Method of Assignment to Treatment

The method of treatment assignment is described in the H0P-MC-CPMP SAP Version 5.

6. A Priori Statistical Methods

6.1. General Considerations

The estimand for the primary clinical question of interest has been described in the H0P-MC-CPMP SAP Version 5.

Other general considerations for analyses are described in the H0P-MC-CPMP SAP Version 5.

6.2. Adjustments for Covariates

The general adjustment strategy has been described in the H0P-MC-CPMP SAP Version 5.

Randomization into H0P-MC-BP01 is stratified by the presence of neuropathic pain as defined by the painDETECT score.

The following stratification factor will be included in the models for the primary, secondary, and some exploratory outcomes.

Neuropathic pain	painDETECT score
Positive presence	≥19
Unclear or negative	<19

6.3. Handling of Dropouts or Missing Data

The missing data strategy has been described in the H0P-MC-CPMP SAP Version 5.

6.4. Multiple Comparisons/Multiplicity

There is no plan to formally adjust for multiplicity.

6.5. Use of an “Efficacy Subset” of Participants

There are no plans to use a modified efficacy subset.

6.6. Participant Disposition

The summary of participant disposition has been described in the H0P-MC-CPMP SAP Version 5.

6.7. Participant Characteristics

The general summary of participant characteristics has been described in the H0P-MC-CPMP SAP Version 5.

ISA-specific considerations are described below.

- painDETECT ≥19 (i.e., Positive for neuropathic pain)
- Roland Morris Disability Questionnaire (RMDQ) Total Score at baseline

6.8. Treatment Compliance

To assess the impact of compliance to the protocol specified dosing schedule, the number of days between each infusion will be summarized and reported by treatment arm. The summaries will include descriptive statistics (sample size at visit, mean, SD, median, minimum, maximum). No inferential statistics will be reported.

6.9. Concomitant Therapy

The summary and reporting of concomitant therapy has been described in the H0P-MC-CPMP SAP Version 5. No additional covariates will be considered in the models of weekly rescue medication use.

6.10. Efficacy Analyses

6.10.1. Primary Outcome and Methodology

The analysis of the primary outcome has been described in the H0P-MC-CPMP SAP Version 5. The longitudinal model will include average NRS during the preliminary data entry period (PDEP) period and within each nominal week of the double treatment period as a longitudinal outcome. As noted in [Section 4.1](#), endpoint for the primary analysis is defined as 8 weeks post initial treatment administration.

6.10.2. Additional Analyses of the Primary Outcome

There are no additional analyses planned for the primary outcome.

6.10.3. Secondary Efficacy Analyses

Secondary efficacy analyses common to all ISAs within H0P-MC-CPMP have been described in the H0P-MC-CPMP SAP Version 5. H0P-MC-BP01 will also consider the following secondary analyses.

The RMDQ is a simple, sensitive, and reliable method to measure disability in patients with back pain. The RMDQ consists of 24 statements relating to the person's perceptions of back pain and associated disability based on

- physical ability/activity
- sleep/rest
- psychosocial
- household management
- eating, and
- pain frequency.

Participants are asked if they feel the statement is descriptive of their own circumstance on that day. The total score is obtained by counting the number of "Yes" responses, ranging from:

0 = no disability to 24 = maximal disability.

A Bayesian longitudinal mixed-effect model repeated measures (MMRM) analysis will be performed to evaluate the change from baseline to each postbaseline visit for the RMDQ total score. The model will utilize the constrained cell means model so that a common mean is estimated at the baseline. More details on this approach are provided in the H0P-MC-CPMP SAP Version 5.

This table describes information included in the model.

Categorical effects	
 the interaction of treatment and timepoint (constrained to estimate a common mean at baseline across treatments) average baseline pain severity category (baseline NRS < 7, baseline NRS \geq 7) presence of neuropathic pain (painDETECT \geq 19, painDETECT < 19) pooled investigative site
Continuous covariates	
 none

Other Secondary Analysis

[figure not shown]
The proportion of participants in each treatment group meeting prespecified binary efficacy outcomes will be calculated for each post baseline time point and will be used to compare treatment groups. The prespecified binary efficacy outcomes include the proportion of participants:

[figure not shown]
- with a reduction greater than or equal to 30%, 50%, and 70% from baseline as measured by the RMDQ score, and
- with at least a 3.5 point reduction from baseline in the RMDQ score.

A Bayesian pseudo-likelihood-based categorical repeated measures regression model that includes all post baseline observations will be used to estimate the probability of achieving the response level in each treatment group and will be used to compare treatment groups.

The model will include the categorical and continuous covariates described for the secondary analysis of RMDQ total score.

In addition, time to first treatment response from baseline based on the prespecified binary thresholds above will be assessed. Analyses will be conducted according to the time to event analyses specified in the CPMP SAP Version 5.

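### As written, the RMDQ responder models contain no baseline RMDQ term, so the treatment difference in response probability may be less precise than it could be

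*SAP*

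**What the plan says.** SAP 4.2 lists the RMDQ endpoints as Other Secondary. Among them are "Proportion of participants with reduction from baseline of at least 3.5 points on RMDQ total score across all time points" and the proportions reaching reductions of 30%, 50% and 70%.

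SAP 6.10.3 specifies two kinds of model.

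- **Total score.** A Bayesian repeated-measures model in which baseline is one of the outcome time points. The treatment-by-timepoint term is "constrained to estimate a common mean at baseline across treatments". The other terms are baseline NRS (below 7, or 7 and above), painDETECT (below 19, or 19 and above) and pooled site. The entry for continuous covariates is none.
- **Responders.** A Bayesian pseudo-likelihood "categorical repeated measures regression model that includes all post baseline observations". It is used to "estimate the probability of achieving the response level in each treatment group" and to compare the groups. Its covariates come by reference: "The model will include the categorical and continuous covariates described for the secondary analysis of RMDQ total score".

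SAP 6.7 summarizes "Roland Morris Disability Questionnaire (RMDQ) Total Score at baseline" as a participant characteristic. SAP 6.2 adds: "The general adjustment strategy has been described in the H0P-MC-CPMP SAP Version 5". That master SAP is not among the documents supplied.

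**The concern.** Listing no continuous covariate is coherent for the total-score model, because baseline RMDQ is already in the outcome vector. The same list does not fit a model without baseline rows. The reference to continuous covariates then points to nothing, and a constraint on the baseline mean has nothing to act on. The list reads as if it had not been adapted to the responder model, although the documents do not prove that.

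Response is defined from baseline, so baseline RMDQ can be prognostic for it. The NRS category measures pain and does not replace a disability score. With about 43 placebo completers, precision is scarce, and a covariate that is already collected would go unused. What is at stake is the spread of the estimated difference in response probability, and therefore power.

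**Working it through.** **1. The plan's own figure.** Protocol synopsis: 150 randomized, 15% dropout. 150 × 0.85 = 127.5, which agrees with the stated 128. At 2:1 this is about 85 and 43. No power or response rate is given for the RMDQ responder endpoints, and the criterion in the sample-size section is redacted.

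**2. When does response depend on baseline?** Write Week 8 RMDQ as W = 9 + s(B − 12) − 2T + e. Here B is baseline (assumed mean 12, SD 5), s the baseline-to-Week-8 slope, T treatment (assumed effect 2 points), and the assumed mean placebo change is −3. All of these are assumptions.

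- 3.5-point response: the drop B − W depends on B with coefficient 1 − s.
- Reduction of at least a fraction q: the condition is (1 − q)B − W ≥ 0, which depends on B with coefficient 1 − q − s.

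| Slope s | 3.5 points | 30% | 50% | 70% |
|---|---|---|---|---|
| 0.4 | 0.6 | 0.3 | 0.1 | −0.1 |
| 0.6 | 0.4 | 0.1 | −0.1 | −0.3 |
| 0.8 | 0.2 | −0.1 | −0.3 | −0.5 |
| 1.0 | 0.0 | −0.3 | −0.5 | −0.7 |

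The 3.5-point response should therefore gain most at a low slope, and the 70% response at a slope near 1. Cells near zero should gain almost nothing.

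**3. Formula check.** If baseline correlates r with response, adjustment multiplies the SE by √(1 − r²), equivalent to dividing n by (1 − r²). Two-sided 5% test of two proportions, placebo n = 42.5, active n = 85. Example with 30% v 50%, pooled rate 0.4333:

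- Null SE = √(0.2456 × (1/42.5 + 1/85)) = 0.0931. Alternative SE = √(0.21/42.5 + 0.25/85) = 0.0888. Power = Φ((0.20 − 1.96 × 0.0931)/0.0888) = 57.8%.
- With r = 0.4, n is divided by 0.84 and the SEs become 0.0853 and 0.0814. Power = 65.6%, a gain of 7.8 points.

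Over response-rate pairs from 25% v 40% to 35% v 62%:

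| r | SE ratio | Power gain (points) |
|---|---|---|
| 0 | 1.00 | 0 |
| 0.1 | 0.995 | 0.3 to 0.4 |
| 0.2 | 0.98 | 1.4 to 1.8 |
| 0.3 | 0.95 | 3.3 to 4.2 |
| 0.4 | 0.92 | 6.0 to 7.8 |
| 0.45 | 0.89 | 7.5 to 10.2 |

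**4. Simulation.** Single visit, RMDQ rounded and limited to 0–24. Logistic model with treatment, NRS category and painDETECT, without and with baseline RMDQ. Residual SD 4.5; sizes 85/43 and 100/50; 4,000 trials per setting. Gain in power (points):

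| Slope | 3.5 points | 70% |
|---|---|---|
| 0.4 | 6.0 to 8.4 | 0.1 to 1.9 (slopes 0.4 to 0.6) |
| 0.6 | 3.9 to 5.0 | as above |
| 0.8 | 1.4 to 2.8 | 2.9 to 4.1 |
| 1.0 | 0.2 to 0.9 | 5.2 to 7.0 |

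The 30% response gains about 0 to 3 at any slope. The 50% response gains 0 to 0.6 at slopes 0.4 to 0.6 and 4.2 to 5.2 at 1.0. The pattern follows the coefficients in step 2.

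At 85/43 the SD of the 3.5-point response difference goes from 9.3/9.1/9.3/9.4 to 8.3/8.7/9.1/9.4 percentage points at slopes 0.4/0.6/0.8/1.0. At slope 0.4, (9.3/8.3)² = 1.26, equivalent to about 26% more participants. At slope 1.0 nothing is gained.

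**5. Sensitivity to the residual SD.** With residual SD 6 and baseline SD 4 or 5, gains are about 3 points or less. The largest cell in a 4,000-trial rerun went from 24.1% to 27.6% (3.5-point response, slope 0.4, baseline SD 5). The SD there still falls, from 9.3 to 8.6. Power moves less because it is low to begin with.

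**6. Closer to the planned model.** Repeated measures with four assumed visits, eight assumed pooled sites and residual SD 4.5. Week 8 power rises from 36.5% to 42.9% (3.5 points, slope 0.4) and from 32.7% to 38.7% (70%, slope 1.0).

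**7. Validity.** With no treatment effect, rejection rates were 3.3–5.5% without and 3.5–5.8% with baseline on the log-odds scale, and 5.3–7.0% and 5.4–7.0% for the response difference. Omitting the term does not inflate type I error.

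Limits: the simulations are frequentist, with no missing data and no true site effect. The planned model is Bayesian.

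**The case against.** The strongest reply is that the general adjustment strategy, the details of the constrained model and the secondary analyses common to all appendices sit in CPMP SAP Version 5. A reader might infer that the omission is established. The documents do not support that, because a baseline term could be added there. This stands, and it makes checking that document the first step.

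Second, the loss is conditional. Several cells show no gain, and the 0-to-8 range comes from one choice of variances. This also stands and is why the point says may. The absolute threshold adds little by itself. On an integer scale a 3.5-point reduction means at least 4, so it cannot be reached from a baseline of 3 or below. Under the assumed mean 12 and SD 5 that is Φ((3.5 − 12)/5) = about 4.5% of participants.

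Third, the models already adjust for NRS category, painDETECT and site, and the total-score model uses baseline RMDQ. That limits the consequence but does not put baseline RMDQ into the responder models.

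Fourth, it may be too late to replace the model. The revision history says "SAP Version 2 was approved prior to unblinding H0P-MC-BP01 data for PoC lock", places Version 3 before final lock, and Section 8 cites analyses already done at PoC lock. This restricts the remedy rather than removing the point.

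**Conclusion.** The point holds as one of possible lost precision. As SAP 6.10.3 is written, baseline RMDQ enters the responder models neither as outcome nor as covariate.

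Under the assumed inputs the power forgone is about 0 to 8 percentage points with residual SD 4.5, and about 3 or less with residual SD 6. It could reach about 10 if baseline correlates 0.45 with response. The slope, the variances and the response rates decide where in that span the trial lies, and the documents give none of them.

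A reader might go on to infer that the treatment comparison is biased or its error rate inflated. Neither follows: randomization protects the comparison, and the null rejection rates are alike with and without the term. Nor is the primary analysis touched. The gain lies in the difference in response probability and in power. The SE of the conditional log-odds ratio actually rises with adjustment (0.39 to 0.45 at slope 0.4), because the adjusted odds ratio is a different, larger quantity. This is a low-priority improvement, stated with medium confidence.

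**What to change.** 1. Check whether CPMP SAP Version 5 already puts baseline RMDQ into categorical responder models, and how it forms response probabilities. If it does both, a cross-reference in 6.10.3 is enough.
2. If the term is absent and PoC treatment data are still blinded, replace the inherited covariate sentence with, for example: *The responder models will include treatment, timepoint, their interaction, baseline NRS category, painDETECT stratum, pooled site and continuous baseline RMDQ total score. Response probabilities and their difference will be averaged over the observed baseline covariates.*
3. If PoC treatment data are already unblinded, keep the current model and report the adjusted one as a labelled sensitivity analysis. Do the same for any RMDQ responder repeats under Section 8. That section lists the 30%, 50% and 70% thresholds for the disease-specific function measure and not the 3.5-point response.

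The averaging rule matters once baseline is in the model. At slope 0.4 the adjusted 3.5-point difference is 14.0 points averaged over observed baselines but 18.3 at mean covariate values.

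Cost: one or two sentences and a little more analysis work, with no new data collection. The model may be unstable with pooled-site effects at the less frequent thresholds, so a fallback for non-convergence should be stated. Replacing the main model after unblinding would break continuity with the PoC results, hence step 3.

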6.12. Safety Analyses

The general analysis of safety has been described in the H0P-MC-CPMP SAP Version 5. However, additional ISA-specific safety considerations are described in the sections below.

6.12.1. Extent of Exposure

The cumulative dosage taken during the double-blind treatment period will be summarized. In addition, the distribution of the number of doses received during the double-blind treatment period will be summarized by reporting the number and percent of participants in the safety population who received 1, 2, 3, or 4 infusions during the double-blind treatment period.

Duration of exposure to study drug (defined as the time since first injection of the study treatment in days) will be summarized by treatment group using descriptive statistics; the summary will also include the total exposure in patient years.

Duration of exposure (days):

$$= \text{Date of last study visit (scheduled or unscheduled) during the double blind treatment period} - \text{Date of first injection of the study treatment} + 1$$

Total exposure in patient years will be calculated as follows:

$$\text{Total exposure in patient years} = \text{Sum of duration (days) of exposures for all patients in the treatment group} / 365.25$$

6.12.2. Adverse Events

The general analysis of adverse events has been described in the H0P-MC-CPMP SAP Version 5.

This ISA will also consider post-treatment-emergent adverse events due to the long follow-up period.

A post-treatment-emergent adverse events (PTEAE) is defined as an event that first occurs or worsens in severity after treatment discontinuation and on or before study discontinuation. The Medical Dictionary for Regulatory Activities (MedDRA) Lowest Level Term (LLT) will be used in the post-treatment-emergent computation. The maximum severity for each LLT during the treatment period will be used as a reference.

The baseline of PTEAE is from the first dosing date to the treatment disposition in the double-blind treatment phase. The post-treatment follow-up period will be included as postbaseline for this analysis. While unusual, it is possible to have a missing severity for events. Events with a

missing severity during the post-treatment period will be treated as “severe” and post-treatment period emergence will be determined by comparing with treatment period. All events occurring after the day of treatment discontinuation will be treated as post-treatment period.

PTEAEs will be summarized by preferred term and by preferred term within system organ class in participants who received LY3016859.

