4.1. Overall Design

The CPMP Master Protocol and CLBP CPMP(2) DSA describes the overall study design and study design rationale. This section describes visits and overall procedures unique to ISA BP01 for LY3016859 in addition to the procedures outlined in the CPMP Master Protocol and CPMP(2) DSA.

Double-blind Treatment Period (Visits 3 through 7)

Each visit is an outpatient visit.

At Visit 3

- participants are randomized to LY3016859 or placebo
- the site completes the BP01 baseline procedures and sample collection
- participants receive their first dose of study intervention via intravenous (IV) infusion over 1 hour
- the site observes participants in the clinic for at least 4 hours after the completion of the IV infusion
- the site completes all post-treatment sample collection and safety monitoring, and
- the site instructs participants to continue with study restrictions and Numeric Rating Scale (NRS) diary entries before their visit discharge.

At Visits 4 through 6

- the site reviews available safety data and completes pre-dose procedures and sample collection
- participants receive an IV infusion over 1 hour
- the site observes participants in the clinic for at least 4 hours after the completion of the IV infusion
- the site completes all post-treatment sample collection and safety monitoring, and
- the site instructs participants to continue with study restrictions and NRS diary entries before their visit discharge.

At Visit 7

- the site completes all procedures and sample collection noted in the schedule of activity (SoA)s
- no intervention is administered at this visit, and
- the site instructs participants to continue with study restrictions and NRS diary entries before their visit discharge.

Post-treatment Follow-up Period (Visits 801-803)

Participants must complete 3 post-treatment follow-up visits for safety, PK, epiregulin PD, and immunogenicity assessment at Visits 801 through 803, according to the SoA.

The site schedules Visit 801 approximately 4 weeks after Visit 7.

At Visit 801, participants return the device for NRS diary collection.

At Visit 803, the participants are discharged from the study.

If the participant receives at least one dose of intervention and discontinues during the double-blind treatment period, they should complete early discontinuation procedures per the CPMP Master Protocol SoA, and Visit 801 should be scheduled approximately 30 days after the last dose of study intervention.

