6.19. Clinical Trial Registry Analyses

Additional analyses will be performed for the purpose of fulfilling the Clinical Trial Registry (CTR) requirements.

Analyses provided for the CTR requirements include the following:

Summary of adverse events, provided as a dataset, which will be converted to an XML file. Both Serious Adverse Events and ‘Other’ Adverse Events are summarized: by treatment group, by MedDRA preferred term.

- A serious adverse event is an adverse event that is considered ‘Serious’ whether or not it is a treatment emergent adverse event (TEAE).
- An adverse event is considered in the ‘Other’ category if it is both a TEAE and is not serious. For each Serious AE and ‘Other’ AE, for each term and treatment group, the following are provided:
 - the number of participants at risk of an event
 - the number of participants who experienced each event term

- the number of events experienced.
- Consistent with www.ClinicalTrials.gov requirements, ‘Other’ AEs that occur in fewer than 5% of participants in every treatment group may not be included if a 5% threshold is chosen (5% is the minimum threshold).
- AE reporting is consistent with other document disclosures for example, the CSR, manuscripts, and so forth.

A summary of a baseline characteristics XML file will be provided.

7. Unblinding Plan

The general unblinding plan is described in the H0P-MC-CPMP SAP Version 5. Unblinding considerations specific to H0P-MC-BP01 are provided below.

Immunogenicity Analysis Planning

To support the assessment committee's evaluation of immunogenicity, a limited number of preidentified individuals may also gain access to the unblinded data. The project statistician will work with the clinical immunogenicity scientist and clinical lab data scientist to determine an appropriate amount of ISA-level data to support this objective. The timing of the transfer of treatment assignment and immunogenicity data will be based on this collaboration. Information that may unblind the study during the analyses will not be reported to study sites or the blinded study team until the study has been unblinded.

8. Reports to be Generated at Final Database Lock

The following analysis will be performed for final database lock.

- Patient disposition - the analysis of patient disposition conducted in POC lock will be conducted for double-blind treatment and safety follow-up period combined (DB plus FU).

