- eCOA compliance - the overall eCOA compliance analysis conducted in POC lock will be summarized for PDEP period plus at each nominal week up to Visit 801.
- Concomitant therapy – the analysis conducted in POC lock will be repeated in DB plus FU period (may also include PDEP) except the listing of rescue medication use above protocol specified limits.
- Efficacy endpoint – The weekly average pain intensity via NRS will be calculated with extension to week 12 (Visit 801). The following analysis will be conducted across all time points in DB plus FU period based on the same model conducted in DB treatment period. Nominal weeks 9-12 in the follow-up period will be derived in a similar way as described in section 6.12.1 of the H0P-MC-CPMP SAP Version 5, except that the days between V7 and V801 are split across 4 weeks.
 - Change from baseline in average pain intensity measured by weekly average of NRS
 - Change from baseline in worst pain intensity measured by weekly average of NRS
 - Change from baseline in DSA-specific physical functioning measures
 - Proportion of participants with a pain reduction from baseline greater than or equal to 30%, 50%, and 70% as measured by the average pain responses on the NRS
 - Proportion of participants with reduction from baseline greater than or equal to 30%, 50%, and 70% on DSA-specific physical function subscale
 - Overall improvement as measured by Patients' Global Impression of Change

A frequentist MMRM analysis will be conducted as a sensitivity analysis for the primary and some secondary endpoints.

A Bayesian MMRM subgroup analysis of baseline pain severity (<7, >=7) will be also evaluated for the primary endpoint. A frequentist MMRM analysis will be performed as a sensitivity analysis for subgroup analysis.

- Safety analyses for TEAEs – the following analysis will be repeated in DB plus FU period unless otherwise specified.
 - Overview of adverse event, a listing of AE (also include PDEP)
 - SAE and a listing of SAE
 - TEAE and post-treatment-emergent adverse event (PTEAE) by PT, by PT within SOC, and PT by maximum severity. A listing of TEAE and PTEAE will be provided.

- Post-treatment-emergent AE by PT, by PT within SOC for safety follow-up period only
- Adverse event of special interest (ISA specific)
- Laboratory measures – some analysis conducted in POC lock will be repeated in DB plus FU period. The additional analysis will be included but not limited to

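### SAP 6.12.2 confines the post-treatment adverse event tables to LY3016859 recipients while Section 8 states no arm, so late events may have no placebo rate beside them

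*SAP*

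**What the plan says.** SAP Section 6.12.2 gives the reason for the analysis: "This ISA will also consider post-treatment-emergent adverse events due to the long follow-up period". It defines a PTEAE as "an event that first occurs or worsens in severity after treatment discontinuation and on or before study discontinuation", which applies equally to either arm. It then limits the tables: "PTEAEs will be summarized by preferred term and by preferred term within system organ class in participants who received LY3016859".

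SAP Section 8, the list of outputs for final database lock, names two sets of PTEAE tables. One is "TEAE and post-treatment-emergent adverse event (PTEAE) by PT, by PT within SOC, and PT by maximum severity", followed by a listing. The other is "Post-treatment-emergent AE by PT, by PT within SOC for safety follow-up period only". Neither entry states an arm.

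Protocol Section 4.1 applies follow-up to everyone: "Participants must complete 3 post-treatment follow-up visits for safety". The Schedule of Activities (Protocol 1.3) has adverse event collection at Visits 801, 802 and 803, with no distinction by arm.

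SAP Section 6.19 covers the registry tables, which are by treatment group. A serious event is included "whether or not it is a treatment emergent adverse event (TEAE"). A non-serious event enters the 'Other' category only "if it is both a TEAE and is not serious".

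**The concern.** A programmer can build the PTEAE tables with one arm or two and find support in the SAP for either. Followed as written, 6.12.2 gives the LY3016859 arm alone.

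That matters because of what the follow-up is for. It takes up most of the study, and Protocol 4.2 says that sampling to 20 weeks after the last dose is meant to characterise safety and immunogenicity. The half-life approaches 18 days at higher doses (Protocol 2.2), and treatment-emergent antibodies were seen in up to 57% of participants after multiple doses (Protocol 2.3.1). Late events are therefore a real question for this product.

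Follow-up also has its own background noise. Participants may go back to standard back pain treatment after Visit 801 (Protocol 2.3.1 and 6.5), so restarted medication can produce adverse events in both arms. A one-arm table cannot separate those from late drug effects. A randomised placebo column shows the background directly.

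**Working it through.** **Step 1: the texts side by side.**

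| Item | Arms stated | Window |
|---|---|---|
| PTEAE definition (SAP 6.12.2) | none; applies to both | after treatment stops |
| PTEAE tables (SAP 6.12.2) | LY3016859 only | after treatment stops |
| PTEAE tables and listing (SAP 8) | none | after treatment stops, including a follow-up-only table |
| AE overview, SAE, TEAE and special-interest outputs (SAP 8) | none | double-blind plus follow-up combined |
| Registry tables (SAP 6.19) | by treatment group | not split by period |

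Only the PTEAE tables isolate follow-up, and the one explicit rule on their arms leaves placebo out.

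**Step 2: denominators.** Inputs are 150 randomised 2:1, that is 100 and 50, and 15% dropout (Protocol 1.1). Completers of the double-blind period: 150 × (1 − 0.15) = 127.5, which reproduces the stated figure of about 128 (SAP 5.2). Split 2:1 this is about 85 and 43. Under 6.12.2 the placebo denominator in the PTEAE tables is 0; with both arms shown it is about 43 to 50. Follow-up is 18 of 26 weeks, or 69% of study time. Weeks 12 to 26, after Visit 801, are 14 of those 18 weeks.

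**Step 3: what a one-arm count can look like with no drug effect.** The documents give no event rates, so I assume a risk p of 2%, 5% or 10% for a preferred term over follow-up. Cases are Binomial(n, p). The table shows the expected count np and the 2.5th to 97.5th percentiles.

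| p | LY3016859, n = 100 | Placebo, n = 50 | LY3016859, n = 85 | Placebo, n = 43 |
|---|---|---|---|---|
| 2% | 2 (0–5) | 1 (0–3) | 1.7 (0–5) | 0.9 (0–3) |
| 5% | 5 (1–10) | 2.5 (0–6) | 4.3 (1–9) | 2.2 (0–5) |
| 10% | 10 (5–16) | 5 (1–9) | 8.5 (4–14) | 4.3 (1–8) |

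**Step 4: what a placebo column adds.** For observed proportions p1 and p0 with Wilson limits (l1, u1) and (l0, u0), and d = p1 − p0, the Newcombe interval is

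- lower = d − √[(p1 − l1)² + (u0 − p0)²]
- upper = d + √[(u1 − p1)² + (p0 − l0)²]

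The Wilson limits are 0.055 to 0.174 for 10/100, 0.133 to 0.289 for 20/100, and 0.043 to 0.214 for 5/50.

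- 10/100 v 5/50: d = 0; 0 ± parts give −12.2 to +9.3 points.
- 20/100 v 5/50: d = +10 points; interval −3.2 to +20.5 points.

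Alone, 10/100 has an exact 95% interval of 4.9% to 17.6% and nothing to set it against.

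**Step 5: the limit of that gain.** Power of a two-sided 5% pooled-variance z test for 20% v 10% is Φ[(d − 1.96·s0)/s1]. With 100 v 50 the pooled proportion is 25/150 = 0.167, s0 = √[0.167 × 0.833 × (1/100 + 1/50)] = 0.0645 and s1 = √[0.2 × 0.8/100 + 0.1 × 0.9/50] = 0.0583. Power = Φ[(0.10 − 0.1265)/0.0583] = 0.325. With 85 v 43 it is 0.281. The comparison can only be descriptive.

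**The case against.** **Section 8 need not conflict with 6.12.2.** It is a list of outputs and states no arm for its other adverse event tables either, so its silence can be read as inheriting the 6.12.2 rule. If it is instead read as unrestricted, the placebo column exists and the harm goes away. This is fair, and it is why the consequence is conditional on 6.12.2 governing. On either reading the text still needs correcting: one gives a follow-up table without a control, the other gives two populations for one analysis.

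**Late placebo events are not lost.** The Section 8 listing states no arm. Setting the double-blind outputs against the combined-period outputs would give a rough follow-up increment by arm. Special-interest events are also repeated over the combined period. This stands as far as it goes. A reader would have to reconstruct the rate, and differencing two tables misses some worsening and repeat events.

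**The master SAP (CPMP SAP Version 5) is not among the documents.** It may set the TEAE window and the table layout. If TEAEs run through follow-up, non-serious late events would enter the combined tables and the registry 'Other' tables by arm, subject to any 5% threshold. That would narrow the gap but not close it, because those tables do not isolate follow-up.

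**The line between serious and non-serious is not drawn by 6.12.2.** True: serious late events also lack a placebo rate in the follow-up-only tables. They have other by-arm reporting, so the greater loss is for non-serious events.

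**The 85 v 43 scenario is not the PTEAE denominator**, because participants who stop treatment early are still scheduled for Visit 801. This is correct. Those figures serve as a cautious lower case only.

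**Conclusion.** The concern holds. SAP 6.12.2 restricts the PTEAE tables to one arm without giving a reason, Section 8 does not restate the population, and the placebo follow-up data will exist. If 6.12.2 governs, the tables that isolate 18 of the 26 study weeks show no background rate. At assumed risks of 2% to 10%, chance alone would give anywhere from 0 to 16 cases of a term among 100 LY3016859 participants, with nothing beside them for comparison.

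This should be changed, but its reach is limited. It affects a descriptive safety display in a Phase 2 study, not the primary analysis, data collection or the by-arm reporting of serious events. The size rests on assumed event rates. The exact extent of the gap depends on the TEAE window and table layout in CPMP SAP Version 5, which I could not see.

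**What to change.** Replace the restricting sentence in SAP 6.12.2 with wording such as:

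> PTEAEs will be tabulated for the safety population by treatment group (LY3016859 and placebo), at preferred-term level and by preferred term nested in system organ class, using the PTEAE period defined above.

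Add to Section 8 that all of its PTEAE tables and the listing follow that rule. State that the comparison between arms is descriptive.

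The cost is one sentence, one cross-reference and one extra column. No new data are needed.
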